8.3 BLINDING PLAN

The investigational agents, bupropion and placebo, will be supplied by the Murty Pharmaceuticals, Inc. in high density polyethylene bottles with child resistant caps that do not reveal the identity of the investigational agent. The bottles will be labeled with a product label and a subject label.

8.4 RANDOMIZATION PLAN

Adaptive random allocation of subjects to study groups was developed to balance groups with respect to screening prognostic variables. The procedure allocates treatment assignment based on the assignments and prognostic variable levels for all previously enrolled subjects. The treatment groups will be balanced with respect to gender, historical self-report of methamphetamine use (prior use in the last 30 days ≤ 18 *versus* > 18), and severity of depression (HAM-D score ≤ 12 *versus* >12). A new subject will be randomized with a "biased coin" procedure, which uses randomization probabilities, favoring the treatment with the deficit enrollment, to improve the balance on group assignment. The randomization process will be performed by KAI.

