3 PROTOCOL SYNOPSIS

STUDY OBJECTIVES: To assess the efficacy and safety of bupropion in reducing methamphetamine use in subjects with methamphetamine dependence. It is hypothesized that bupropion treatment, compared to placebo, will be associated with fewer days of methamphetamine use as measured by quantitative urine analysis for methamphetamine.

STUDY DESIGN: This is a double-blind, placebo-controlled, parallel-group design study in which, after screening and a 2-week baseline period, 150 subjects will be randomly assigned to either placebo or bupropion for 12 weeks with a follow-up assessment 4 weeks after treatment completion. Five clinical research sites will each recruit approximately 30 participants into the trial. Adaptive randomization will be used to balance treatment groups based on gender, historical self-report of methamphetamine use (prior use in the last 30 days \leq 18 *versus* > 18), and severity of depression (HAM-D score \leq 12 *versus* >12).

STUDY POPULATION: 150 individuals (30 per site) with Diagnostic and Statistical Manual of Mental Disorders Fourth Edition (DSM-IV) criteria for methamphetamine dependence determined by structured clinical interview (SCID) will be randomized into one of two treatment groups. Males and females, between 18 and 65 years-of-age, with 1 methamphetamine positive urine specimen provided during the 2-week baseline period prior to randomization who verbalize the ability to understand and provide written informed consent will be included.

TREATMENTS: Subjects randomized to bupropion treatment will receive 150 mg of sustainedrelease bupropion once daily for 3 days then twice daily for a total of 300 mg for a total of 12 weeks (dose taper will be performed the last 3 days of the 12 weeks to 150 mg per day). Subjects randomized to the placebo arm will receive matched placebo tablets according to the same schedule. All subjects will receive manual-guided cognitive behavioral therapy (CBT) thrice weekly during the 12 weeks of treatment.

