11.2 COGNITIVE BEHAVIORAL THERAPY

The CBT program will consist of thrice weekly, 90-minute group sessions through the 12-week trial. However, in order to help potential participants to stop methamphetamine use, they will be introduced to the counselors and scheduled to attend two 60-minute early recovery skills groups each week after signing informed consent up until study enrollment. Topics covered in this early recovery skills group include: Getting Rid of Paraphernalia; Triggers; Introduction to 12-Step Groups; and Brief Information on HIV (see Appendix II). Concepts presented in these sessions include the following: (1) self-monitoring and relapse analysis; (2) identification of "triggers" and cognitive strategies for coping with them; (3) teaching of problem solving skills; (4) education about methamphetamine and methamphetamine dependence; (5) education about HIV and reducing the risk of HIV transmission; and, (6) promotion of prosocial activities. The content of these group topics is prearranged and sequenced using a manualized format. This is a feasible treatment that is known to be well accepted by subjects and it represents an appropriate, ethically defensible standard treatment condition to serve as the "platform" for the medication trial. Staff members who provide CBT counseling will have attended training in the use of these materials. The CBT specialist will have a minimum of a master's degree (or equivalent) or a bachelor's degree plus counseling experience with substance users. To ensure that the integrity of these sessions is maintained, all sessions are audiotaped and reviewed centrally by the Principal Investigator or his designee. Our experience is that these sessions are valued by subjects and attendance is excellent. Thus, psychosocial involvement is seen as a standard or platform for the proposed pharmacotherapy evaluation.

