15.6 ANALYSIS PLAN

15.6.1 Efficacy Assessments

Each of the primary and secondary efficacy outcome measures will be analyzed for the intent-totreat and for the evaluable population. Major differences in the results, if any, will be further explored. While there is every intent to be complete in describing the analyses to be performed, it is not possible to anticipate every contingency and some adjustments may be required to meet constraints posed by the structure of the data.

Statistical tests will be two-sided at a 5% Type I error rate. Confidence intervals will be two-sided with a 95% confidence coefficient.

Primary Efficacy Outcomes

The weekly mean proportion of methamphetamine-free urines on study will be compared between treatment groups using Generalized Estimating Equations (GEE) for ordinal categorical response (Lipsitz *et al.*, 1994). GEE provide a model-based regression method applicable for the analysis of the correlated data that will result from this repeated measures longitudinal study. The GEE procedure was first proposed by Liang and Zeger (1986) and Zeger and Liang (1986) and models the population average. GEE has several useful features:

- 1. It can be used to analyze different types of outcomes such as continuous, binary, or count.
- 2. It can be used to analyze an unbalanced design caused by either differing numbers of observations per person or by observations taken at different times.
- 3. The parameter estimates are consistent even if assumptions about the variance structure are not completely accurate.

As a secondary analysis, the individual effects, if any, of age, race, site, and usual route of methamphetamine use (oral/nasal inhalation versus intravenous/smoked) on the primary treatment effects will be determined where numbers permit. The first order interactions of these variables with gender, historical self-report of methamphetamine use (prior use in the last 30 days ≤ 18 versus > 18), and severity of depression (HAM-D score ≤ 12 versus >12) will also be included in the model. Presentation will include the full model with all terms and a reduced model containing only significant terms.

Secondary Efficacy Outcomes

Unless the primary response analysis implies the need for a more elaborate model, between group comparisons of the secondary outcomes will be performed as follows:

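### Clinical site is neither a balancing factor in the allocation nor a term in the primary model, so chance imbalance within sites adds modest, avoidable noise to the arm comparison

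*Protocol*

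**What the plan says.** Section 8.4 sets out a central biased-coin procedure, "which uses randomization probabilities, favoring the treatment with the deficit enrollment". It names three factors: "The treatment groups will be balanced with respect to gender, historical self-report of methamphetamine use" (18 days or fewer against more than 18 in the last 30) and HAM-D score (12 or below against above 12). The synopsis (section 3) and section 8.1 give the same three. Section 12.3 says the randomisation form carries the stratification variables but adds none.

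On sites, the synopsis says "Five clinical research sites will each recruit approximately 30 participants into the trial". Section 7 places them in Missouri, Hawaii, Iowa and two California cities. On background treatment, section 11.2 says "The CBT program will consist of thrice weekly, 90-minute group sessions through the 12-week trial".

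On analysis, section 15.6.1 says that the primary outcome "will be compared between treatment groups using Generalized Estimating Equations (GEE) for ordinal categorical response", with no site term named. Site then appears in a separate sentence: "As a secondary analysis, the individual effects, if any, of age, race, site, and usual route of methamphetamine use", to be examined as far as subject numbers allow. Section 16.3 says the statisticians will follow the protocol's own analytical section.

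**The concern.** Site could plausibly matter to clean-urine rates and retention in this trial. Each clinic runs its own therapy groups with its own counsellors (11.2). Subjects are expected to resemble the local clientele (section 9). Investigators have discretion to terminate subjects (12.12.1). Section 4 itself argues that weak psychosocial support drives early termination and distorts conclusions about the medication.

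If the arms are uneven within sites, part of the observed arm difference is a difference between clinics, arising by chance. With neither balance at allocation nor a site term in the primary model, that component stays in the primary estimate. The secondary look at site would also rest on lopsided cells. Section 15.7 gives no power calculation for 150 subjects, reports 46–50% dropout, and enlarges the trial to make the evaluation more certain, so avoidable noise works against the stated aim.

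**Working it through.** **Inputs from the protocol:** 5 sites of about 30, and 5 × 30 = 150, which matches the planned total; three balancing factors; two arms, taken as 75 each.

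**Assumptions, because the protocol gives no values:** coin probability 0.67 to 0.90; factor prevalences 35%, 50% and 40%; site share of outcome variance 5% to 10%; a continuous outcome with SD 1 standing in for the ordinal GEE.

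**Step 1: benchmark with simple allocation that ignores site.** For one site of 30, the two-sided binomial probability of 20:10 or worse is 0.0987. For at least one of five sites it is 1 − (1 − 0.0987)^5 = 0.405. This is an upper reference only, because the protocol does not use simple randomisation.

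**Step 2: the stated three-factor biased coin, simulated (4,000 trials per setting).**

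| Coin | Some site 20:10 or worse, site not balanced | Same, site balanced from the first subject |
|---|---|---|
| 0.67 | 27.1% | 2.5% |
| 0.80 | 27.7% | 0.1% |
| 0.90 | 26.8% | 0% |

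Without site balancing, the median worst site is 19:11 and the 95th percentile is 21:9. The within-site arm difference has SD about 4.9 subjects.

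**Step 3: shift in the arm difference.** With d the within-site arm difference, the SD of the shift is approximately √5 × SD(d) / 75 × between-site SD. This gives √5 × 4.9 / 75 = 0.146; direct simulation gives 0.147.

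**Step 4: compare with sampling error.** The variance of the difference at 75 per arm is 2/75 = 0.0267 (standard error 0.163).
- Site share 5%: 0.147² × 0.05 = 0.00108, and 0.00108 / 0.0267 = 4%.
- Site share 10%: 0.147² × 0.10 = 0.00216, and 0.00216 / 0.0267 = 8%.

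On the outcome scale, an assumed between-site SD of 0.15 in the proportion of clean urines gives 0.147 × 0.15 = 2.2 percentage points (0.7 to 2.9 for SDs of 0.05 to 0.20).

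**Step 5: type I error.** The unadjusted test rejected in 4.4% to 5.7% of null trials across coins and site shares of 0, 5% and 10%.

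**Step 6: what each remedy recovers.** Adjusting for site removes the shift but loses (SD(d)/30)² of the information: (4.9/30)² = 2.7%.
- Site share 5%: unadjusted variance 0.95 × 0.0267 + 0.00108 = 0.0264; adjusted 0.95 × 0.0267 / (1 − 0.027) = 0.0260. Net gain about 1.5%.
- Site share 10%: unadjusted 0.90 × 0.0267 + 0.00216 = 0.0262; adjusted 0.90 × 0.0267 / (1 − 0.027) = 0.0247. Net gain about 6%.
- No site effect: adjustment costs about 2.7%.

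Balancing on site from subject 51 with a coin of 0.75 reduces SD(d) to about 2.4, so the loss becomes (2.4/30)² = 0.6%. The further gain is 2.7% − 0.6% = about 2%, or some three subjects of 150.

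**The case against.** The strongest case is that nothing here is an error. The three passages on allocation agree, and the choice of balancing factors is a design judgement. Therapy follows a sequenced manual, is given by trained staff, and is audiotaped and reviewed centrally (8.1, 11.2), which may keep site differences small. On the stated method about 73% of trials have no site at 20:10 or worse, and 4–8% of the variance is only about 2–4% on the standard error. With about half the subjects dropping out, balance at entry would not guarantee balance among completers. Covariates are also often left to a statistical analysis plan, which is not available here.

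Most of this stands, and it limits the point to precision. The last argument does not dispose of it: section 15.6.1 does not stay silent on site but assigns it to a secondary analysis, and 16.3 ties the analysis to that section.

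A reader might infer that site differences systematically confound or bias the primary result. The documents do not support that: allocation takes no account of site, so the imbalance is random in direction and the false-positive rate holds. Nor should the 41% binomial figure be quoted as the risk in this trial, since it belongs to a method that the protocol does not use.

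**Conclusion.** The point holds as a modest loss of precision. Site is absent from the allocation factors and from the primary model as described, and about 27% of trials run this way would have some site at 20:10 or worse; that figure barely depends on the coin. The noise added is about 4–8% of the variance of the arm difference if site explains 5–10% of outcome variance. The protocol supplies no between-site figure, coin probability or factor prevalences, and the calculation uses a continuous stand-in for the ordinal outcome, so the size is indicative. If sites hardly differ, there is almost nothing to recover and adjustment costs slightly more than it returns. The case for adjusting is that it guards against the less favourable possibility and answers in advance whether chance imbalance between clinics explains the result.

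**What to change.** In section 15.6.1, specify that the primary GEE includes clinical site as a main effect together with the three balancing factors (gender, prior use, HAM-D category), and keep the secondary analysis for effects of site on the treatment difference. The cost is four extra parameters for site and the small information loss shown in step 6; no extra subjects or visits are needed.

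Optionally, in section 8.4 and the matching sentences of sections 3 and 8.1, add site as a fourth biased-coin factor for subjects still to be randomised. Once site is in the model this gains only about a further 2% of information. It changes the algorithm mid-trial, requires an amendment with IRB approval before use (14.2), and slightly loosens balance on the other three factors. At least 50 subjects were already randomised by the April 2004 review (15.7), and how many more is not stated, so the gain may be smaller than the subject-51 calculation suggests. If only one change is made, it should be the model term.

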8.5 CONCURRENT CONTROLS

As the study design is double-blind (neither the investigator nor the subject know the treatment arm assignment), subjects in the control arm will be given a matching placebo agent along with CBT according to the same schedule as those in the treatment arm.

8.6 DEFINITION OF STUDY POPULATIONS

The intent-to-treat study population is defined as the subjects who provide informed consent, and are enrolled, randomized, and receive at least one dose of investigational agent. The evaluable study population is defined as the subjects who are eligible to participate in the study in accordance with the inclusion and exclusion criteria, complete randomization, and provide at least 6 urine specimens and 28 days of self-report of substance use after enrollment.

9 SUBJECT IDENTIFICATION

Approximately, 30 male and female subjects with methamphetamine dependence will be randomized and enrolled at each study site (150 total). Entry into this study is open to both men and women and to all racial and ethnic subgroups. It is expected that the demographics of participants who participate in this project will reflect the overall gender and ethnic characteristics of the clinic clientele. Participation of women and minorities in this project will be encouraged. Attempts will be made to enroll at least 30% female subjects at each study site.

Subjects will be recruited from a variety of sources. The primary source will be subjects seeking treatment for methamphetamine dependence at each clinic. Additional subjects will be recruited from the community by means of referrals from local treatment providers, advertising in local media, and word of mouth among subjects themselves. Recruitment advertisements will be approved by each site's Institutional Review Board (IRB).

9.1 INCLUSION CRITERIA

Participants must:

- 1. Be males and/or females, between 18 and 65 years-of-age.
- 2. Have a DSM-IV diagnosis of methamphetamine dependence as determined by SCID.
- 3. Have at least 1 amphetamine or methamphetamine positive urine specimen (> 1000 ng/mL) within the two-week baseline period prior to randomization with a minimum of 4 samples tested.
- 4. Be willing and able to comply with study procedures.
- 5. Be able to verbalize understanding of consent form, able to provide written informed consent, and verbalize willingness to complete study procedures.
- 6. Be seeking treatment for methamphetamine dependence.
- 7. If female, have a negative pregnancy test and agree to use one of the following methods of birth control:
 - a. oral contraceptives
 - b. patch
 - c. barrier (diaphragm or condom) with spermicide or condom only
 - d. intrauterine progesterone or non-hormonal contraceptive system
 - e. levonorgestrel implant
 - f. medroxyprogesterone acetate contraceptive injection
 - g. surgical sterilization
 - h. complete abstinence from sexual intercourse

9.2 EXCLUSION CRITERIA

Participants must not:

- 1. Have current dependence, defined by DSM-IV criteria, on any psychoactive substance (i.e., opioids) other than methamphetamine, nicotine, or marijuana or physiological dependence on alcohol or a sedative-hypnotic, e.g. a benzodiazepine that requires medical detoxification.
- 2. Have a current or past history of seizure disorder, including alcohol- or stimulant-related seizure, febrile seizure, or significant family history of idiopathic seizure disorder.
- 3. Currently be using drugs that lower seizure threshold.
- 4. Have a history of head trauma that resulted in neurological sequelae (e.g., loss of consciousness greater than 5 minutes, or that required hospitalization).

- 5. Have psychiatric disorders, such as major current depression, psychosis, bipolar illness, organic brain disorder, or dementia as assessed by the SCID interview, which require ongoing medication treatment or which would make medication compliance difficult. Have had electroconvulsive therapy within the past 90 days before screening, or have a history of Bipolar I Disorder (see Notes).
- 6. Have a current suicidal ideation/plan as assessed by the SCID interview or HAM-D question #3. Current is identified as within the past 30 days.
- 7. Have a current or past history of anorexia nervosa or bulimia disorder.
- 8. Have serious medical illnesses or neurological disorders including, but not limited to, uncontrolled hypertension, significant heart disease (including myocardial infarction within one year of enrollment), angina, hepatic or renal disorders, renal insufficiency (plasma creatinine > 1.7 mg/dL), Parkinson's disease, active syphilis that has not been treated or refuse treatment for syphilis (see note), or have had therapy with any opiate-substitutes (methadone, LAAM, buprenorphine) within 2 months of enrollment, or any serious, potentially life-threatening or progressive medical illness other than addiction that may compromise subject safety or study conduct. Any ECG/cardiovascular abnormality (e.g., QTc interval prolongation > 450 milliseconds in men or 480 milliseconds in women), which in the judgment of the investigator is clinically significant.
- 9. Have diabetes with unstable control of blood glucose and have any incidence of hypoglycemia in the past year before screening.
- 10. Be mandated by the court to obtain treatment for methamphetamine-dependence where such mandate required the results of urine toxicology tests to be reported to the court.
- 11. In the opinion of the investigator, be expected to fail to complete the study protocol due to probable incarceration or relocation from the clinic area.
- 12. Be undergoing HIV treatment with antiviral and/or non-antiviral therapy.
- 13. Have AIDS according to the current CDC criteria for AIDS-MMWR 1999; 48 (no, RR-13:29-31).
- 14. Have CD4 (+) T-lymphocytes blood counts <500 cells/mm³.
- 15. Have known or suspected hypersensitivity to bupropion.
- 16. Be using bupropion or any medication that could interact adversely with bupropion, within the following times of beginning of administration of bupropion based on the longest time interval of A, B, and C, below or as otherwise specified:

- A) Five half lives of other medication or active metabolite(s), whichever is longer;
- B) Two weeks; or
- C) Interval recommended by other medication's product labeling.

Medications that fall into this category include:

- a. Bupropion (Wellbutrin[®], Zyban[®]) used during the past 30 days
- b. All antidepressants
- c. Neuroleptics
- d. Systemic corticosteroids
- e. Xanthines, i.e., theophilline, theophilline sodium glycinate and aminophylline
- 17. Have participated in any experimental study within 8 weeks (the nature of excluded studies may be discussed with NIDA investigators).
- 18. Be pregnant or lactating.
- 19. Have clinically significant laboratory values (outside of normal limits), in the judgment of the investigator (Appendix I).
- 20. Have active tuberculosis (positive tuberculin test and confirmatory diagnostic chest x-ray).
- 21. Have a diagnosis of adult (i.e., 21 years or older) asthma, or chronic obstructive pulmonary disease (COPD), including those with a history of acute asthma within the past two years, and those with current or recent (past 3 months) treatment with inhaled or oral beta-agonist or steroid therapy (because of potential serious adverse interactions with methamphetamine).
- 22. For subjects suspect for asthma but without formal diagnosis, 1) have a history of coughing and/or wheezing, 2) have a history of asthma and/or asthma treatment two or more years before, 3) have a history of other respiratory illness, e.g., complications of pulmonary disease (exclude if on beta-agonists), 4) use over-the-counter agonist or allergy medication for respiratory problems (e.g., Primatene Mist): a detailed history and physical exam, pulmonary consult, and pulmonary function tests should be performed prior to including or excluding from the study, or 5) have an FEV₁ <70 %.

Notes on inclusion/exclusion criterion: Although AIDS is an exclusion criteria, a positive antibody titer to HIV is not. Prospective subjects will be offered HIV testing during screening but may not have the test performed until after enrollment. This test is offered as a courtesy to the prospective subjects along with HIV education.

Prospective subjects who are positive for syphilis by the RPR test will have a fluorescent treponemal antibody absorbent assay (FTP-abs) or microhemagglutinin assay-Treponema pallidum (MHA-TP) confirmatory test performed. If this test is positive, prospective subjects

must be treated for syphilis. If the prospective subject can provide evidence that they have been previously treated for syphilis or undergoes treatment for syphilis, they can be enrolled upon providing proof of successful treatment for syphilis.

The infectious disease panel for hepatitis and tuberculosis is performed as an aid to determine if the prospective subject has active hepatitis or tuberculosis. Either will exclude the prospective subject from participation according to exclusion criterion number 8 (serious medical illnesses) or number 20 (have active tuberculosis). All subjects who test positive for tuberculin PPD will be referred and scheduled to have a chest X-ray. Those that do not actually have tuberculosis will not be excluded from the study. Those that show a positive chest X-ray for tuberculosis will be excluded from the study. Prospective subjects who test positive for hepatitis will be evaluated by the site investigator for eligibility. Those subjects will be excluded if they have acute hepatitis or chronic active hepatitis, based on symptoms serology, and/or abnormal liver functions (see Appendix I). Subjects who test positive for hepatitis will be referred for treatment as well as those who show positive chest X-ray for tuberculosis.

If any test results are positive subject will be notified of positive and confirmatory test results and will be referred to treatment.

Methamphetamine induced psychosis does not exclude a candidate from the study, however the presence of current psychotic symptoms will exclude a candidate from the study until clinically stabilized.

Bupropion is an antidepressant, so depressed subjects will be receiving effective treatment, granted some subjects will be randomized to placebo. This is not different from randomized double-blind trials for major depression. By monitoring subjects closely both clinically and through biweekly HAM-D scores, if we see deterioration in depression or emergence of suicidal ideation, subjects will be excluded from the study and referred for treatment.

